6.2 Dosage, Preparation and Administration of Investigational Product

6.2.1 Challenge and Re-challenge with RV

The challenge viruses to be used in this study are human RVs A16 and A39. Both of these challenge pools are used under FDA regulation (IND 12934 for RV39 and IND 15162 for RV16). Both pools have a concentration of 3.9×10^4 TCID₅₀/mL. The virus stock is diluted into Lactated Ringer's (LR) solution for human parenteral administration to provide a final concentration of 20-100 TCID₅₀/mL for the inoculation. Following a nasal wash, each subject will be given the challenge virus by intranasal drops. The virus is administered in a volume of 0.25 mL/nostril with a calibrated pipette. The 0.25 mL inoculum is administered twice in each nostril 1-3 minutes apart to provide the total virus inoculum. The lot number of the LR solution will be recorded and the virus challenge material will be back-titrated to document the continued potency of the challenge pool.

6.2.2 Modification of Investigational Product for a Participant

There will be no modification of dose in this study. Only one dose of virus is delivered for each challenge.

6.3 Accountability Procedures for the Investigational Product(s)

This study is being conducted by the sponsor-investigator. The investigational product will be under the control of the sponsor-investigator at all times. A dispensing log will be maintained to document administration of the challenge virus to the individual subjects. The investigator will administer the challenge virus. There will be no shipping or distribution of the investigational product.

6.4 Assessment of Subject Compliance with Investigational Product

Compliance is assured since the product is administered to the volunteer by the investigator.

6.5 Concomitant Medications/Treatments

Volunteers who use any common cold therapies in the 2 weeks prior to the study (see list below*) will be excluded from study participation.

* non-steroidal anti-inflammatory medications, benedryl and other antihistamines, Sudafed, pseudoephedrine, phenylephrine, oxymetazoline, inhaled/intranasal steroids, leukotrienes, any bronchodilators (such as short acting b-2-agonists, long-acting b2-agonists, anticholinergics), or dietary supplements.

In the 5 days after each RV challenge the volunteers will be asked to refrain from the use of common cold therapies (see list below*) to avoid interference with assessment of the endpoints of the study. * non-steroidal anti-inflammatory medications, benedryl and other antihistamines, Sudafed, pseudoephedrine, phenylephrine, oxymetazoline, inhaled/intranasal steroids, leukotrienes, or any bronchodilators, (such as short acting b-2-agonists, long-acting b2-agonists, anticholinergics).

All medications used by the volunteers during the study (Day -14 through week 15 post second RV challenge) will be recorded to assist with assessment of compliance and to permit assessment of the symptoms and symptom scoring (See Section 8.2.2).

7 STUDY SCHEDULE

7.1 Study Schedule

Each challenge cohort will be conducted on an identical schedule of events. Volunteer interactions in each cohort are illustrated in the Study Schedule Table in Appendix A

7.2 Screening

7.2.1 Screening and Enrollment Visit (Study day -14 to -7, study visit 1)

- Review study and obtain informed consent (volunteers who consented are provided with a copy of the signed consent)
- Assessment of inclusion/exclusion criteria
- Recording of demographic data to include date of birth, gender, race and ethnic origin
- Complete and review medical history questionnaire
- Vital signs to include pulse, respiratory rate, blood pressure, temperature
- Blood specimen for HLA typing, hemoglobin, total IgE, and RV serology (neutralizing antibody and capsid protein-specific IgG and IgA) (30 ml)
- Blood specimen for baseline PBMC collection (90 ml)
- Recording of concomitant medications.

7.3 First Virus Challenge

7.3.1 Study day 0 (study visit 2)

- Baseline symptom assessment
- Review of interval medical history
- Review of AEs
- Review of concomitant medications
- Blood draw for acute serology and PBMC collection (105 ml)
- Nasal lavage for respiratory virus PCR, and cytokines
- Urine pregnancy screen for females who are not surgically sterile or post-menopausal (results must be known prior to the RV Challenge) Challenge with RV

7.3.2 Study days 1-5 (study visits 3-7)

- Daily symptom assessment
- Assessment of subjective feeling of a cold (day 5 only)
- Daily assessment of AEs
- Daily assessment of concomitant medications
- Daily nasal lavage for RV qPCR, quantitative RV culture, and cytokines

7.3.3 Study day 7 (study visit 8)

- Review of AEs
- Review of concomitant medications
- Blood draw for PBMC collection and RV serology (105 ml)

7.3.4 Study day 14 (study visit 9)

- Review of AEs
- Review of concomitant medications
- Blood collection for RV serology (15 ml)

7.3.5 Study day 28 ± 2 (study visit 10)

- Review of AEs
- Review of concomitant medications
- Blood draw for PBMC collection and RV serology (105 ml)

7.3.6 Study day 63 ± 2, Week 9 (study visit 11)

- Review of AEs
- Review of concomitant medications
- Blood collection for RV serology (15 ml)

7.3.7 15 Weeks after Virus Challenge (study visit 12)

(Note that this visit coincides with Study day 0 for the second virus challenge.)

- Review of AEs
- Review of concomitant medications
- Blood draw for RV serology and PBMC collection (105 ml)

7.4 Second Virus Challenge**7.4.1 Study day RC0 (study visit RC 1)**

- Baseline symptom assessment
- Review of interval medical history
- Urine pregnancy screen for females who are not surgically sterile or post-menopausal
- Review of AEs
- Review of concomitant medications
- Nasal lavage for respiratory virus PCR, and cytokines
- Challenge with RV

7.4.2 Study days RC1-RC5 (study visits RC 2-6)

- Daily symptom assessment
- Assessment of subjective feeling of a cold (day 5 only)
- Daily assessment of AEs
- Daily reassessment of concomitant medications
- Daily nasal lavage for RV qPCR, quantitative RV culture and cytokines

7.4.3 Study day RC7 (study visit RC 7)

- Review of AEs
- Review of concomitant medications
- Blood draw for PBMC collection and RV serology (105 ml)

7.4.4 Study day RC14 (study visit RC 8)

- Review of AEs
- Review of concomitant medications
- Blood collection for RV serology (15 ml)

7.4.5 Study day RC28 ± 2 (study visit RC 9)

- Review of AEs
- Review of concomitant medications
- Blood draw for PBMC collection and RV serology (105 ml)

7.4.6 Study day RC63 ± 2, RC Week 9 (study visit RC 10)

- Review of AEs
- Review of concomitant medications
- Blood draw for RV serology (15 ml)

7.4.7 15 Weeks after Second Virus Challenge (study visit RC 11)

- Review of AEs
- Review of concomitant medications
- Blood draw for PBMC collection and RV serology (105 ml)

7.5 Follow-up

Volunteers will be followed for 15 weeks after each virus challenge as described in sections 7.2 and 7.3.

7.6 Final Study Visit

The final study visit will occur at week 15 after the second virus challenge. The procedures done at this visit are described in section 7.3.7. We will not collect AEs beyond this visit.

7.7 Early Termination Visit

If a volunteer withdraws or is removed from the study due to an AE as described in section 9.1, we will continue to follow the subject until the appropriate resolution of the AE. Early termination due to withdrawal of consent will require no further follow-up or procedures. However, in the event of early termination due to an AE or any other cause, the subject may be asked whether they consent to continue the remaining study procedures.

7.8 Unscheduled Visit

If an unscheduled visit occurs, it will be documented in the notes section of the DCF.

8 STUDY PROCEDURES/EVALUATIONS

8.1 Clinical Evaluations

8.1.1 Medical history

A medical history will be obtained at the time of the enrollment visit. The history is obtained via questionnaire in an interactive interview with a member of the study staff who is a health care professional. The information is recorded on a structured source document to be reviewed by the PI for eligibility prior to enrollment. The medical history will include the use of prohibited medications in the 2 weeks prior to enrollment. Medical records will not be reviewed.

8.1.2 Vital Signs

Vital signs will be done at the enrollment visit.

8.1.3 Concomitant medications

Volunteers will be asked to report all medication use during an interactive interview with the study staff. This information will be collected at each study visit and will be used to assist with assessment of compliance and to permit assessment of the symptoms, symptom scoring, and study analyses. Use of cold medications could impact eligibility (see Section 5.3.1 and Section 6.5), and will impact symptom scoring (see Section 8.2.2).

8.2 Study Procedures

8.2.1 Nasal Lavage

Nasal lavage will be collected for quantitative viral cultures, viral PCR and qPCR, and for determination of cytokine concentrations. These specimens are collected by instillation of 5 mL of sterile 0.9% saline into each nostril. This wash is then immediately expelled into a waxed paper cup and kept chilled until processed. Lavage for viral culture is diluted 3:1 in 4X concentrated viral collection broth and then frozen at -80 °C until cultured for detection of RV. Lavage for cytokine assays is stored undiluted at -80 °C.

8.2.2 Symptom Scoring

Symptom assessment will not be the primary outcome variable for any of the experiments in this proposal. Symptom assessment will be done as part of the secondary analysis of the correlation between different T-cell subsets and symptomatic illness following homologous or heterologous re-challenge.

Volunteers will be asked to refrain from the use of common cold therapies during the 5 days after each RV challenge. Symptom scoring is done using a standardized method [31, 32]. Each

subject is asked in an interactive interview to assess the severity of the symptoms of rhinorrhea, nasal obstruction, cough, sore throat, sneezing, headache, malaise and chilliness as follows:

- **Absent** (0 points)
- **Mild** (1 point) Barely noticeable, does not interfere with daily activity.
- **Moderate** (2 points) Noticeable, but does not prevent daily activity.
- **Severe** (3 points) Interferes or prevents daily activity; or the volunteer used the cold medications listed below* to treat cold symptoms,
 - * non-steroidal anti-inflammatory medications, benedryl and other antihistamines, Sudafed, pseudoephedrine, phenylephrine, oxymetazoline.
 - Or any use of bronchodilators, leukotrienes, or inhaled/intranasal steroids.

The symptom scores will be recorded prior to the nasal wash procedure on Study Days 0-5.

Symptom scores will be collected on Days 0-5, however only the scores on Days 1-5 will be used to calculate the Total Symptom Score (TSS).

8.2.3 Assessment of infection and illness

Volunteers who have challenge virus detected in nasal lavage by culture or PCR on any of the Study Days 1-5 after virus challenge and/or have a four-fold rise in neutralizing antibody titer to the study virus are considered infected. Volunteers who have a positive culture for the challenge virus on any of the Study Days 1-5 after virus challenge are defined as “virus shedders” and the time from Day 0 to the first positive virus culture is defined as the “time to virus shedding”.

The total symptom score will be the sum of the symptom scores for all symptoms on Study Days 1-5. Infected volunteers who have a total symptom score of at least 6 and either at least 3 days of rhinorrhea or the subjective impression that they have had a cold will be defined as having a symptomatic infection.

8.3 Laboratory Evaluations

8.3.1 Virology

Detection of virus in the Study day 0 nasal lavage is done by a multiplex PCR (Luminex xTAG[®] Respiratory Viral Panel [Austin, TX]) in the Clinical Laboratory of the UVA Medical Center.

RV cultures will be done by routine methods [33]. Nasal lavage collected on Study days 1-5 are cultured for RV by inoculation into two tubes of human embryonic lung fibroblast cells (either MRC-5 or WI-38) and incubation on roller drums at 33 °C for 14 days. RV is identified by the development of typical cytopathic effect. One isolate from each subject who sheds virus is confirmed as the challenge RV serotype by a neutralization assay with HRV type 39 or type 16 antiserum. Subjects who have at least one positive culture for the challenge virus or who have at least a four-fold rise in antibody titer to RV type 39 are considered infected. Previous studies have established that the challenge inoculum is not re-isolated from uninfected volunteers, thus a single positive culture is evidence of virus replication in the upper respiratory tract [34]. Serial 10-fold dilutions of the nasal lavage will be cultured in microtiter plates for semi-quantitative determination of viral shedding. Titers are calculated using the method of Karber.

We will use a qPCR assay that has been previously described by other members of our research group [35]. Briefly, RNA is extracted using QIAamp RNA isolation kits (Qiagen, Crawley, UK) and cDNA is generated. The cDNA is amplified using primers and probes specific for conserved regions of RV and detected by qPCR (RV forward 5'-GGCCCTGAATGTGGCTAA-3'; RV reverse 5'-ATCCCCGCAATTGCTCGTTAC-3'; probe 5'-FAM/ CTTGCAGCCAATGCA-BHQ-3') (Integrated DNA Technologies, Coralville, IA). Virus quantity is determined by comparison to a standard curve.

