3.2 Study Outcome Measures

3.2.1 Primary Outcome Measures

Correlation between the number of pre-existing RV-16-specific T cells at Week 15, and infection after homologous re-challenge with RV-16 or infection after heterologous re-challenge with RV-39 at Week 15.

Numbers of pre-existing RV-specific T cells at Week 15 will be determined by MHCII tetramer staining followed by flow cytometry analysis. Infection will be determined by isolation of virus in culture. Infection will be defined as one positive RV culture obtained in the 5-day time interval after virus re-challenge at Week 15.

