9.2.1 Historical performance of the challenge model

The experimental RV challenge model is a well-established model that has been used for the study of the pathogenesis and treatment of rhinovirus infections since the 1960s. There have been a number of variations on the model but the proposed procedures and evaluations in this protocol (described in section 8.2 above) and have been used by the PI for 35 years. Under these conditions, the expected infection rate for volunteers in the study is 85-90%. Mean symptom scores for the RV39 used in the study have typically been in the range of 14-18 with standard deviations of ± 13 . The mean total symptom scores for the RV16 was 20 ± 10 in the initial evaluation of the challenge pool.

The investigators are not aware of any previous rhinovirus challenge study that was discontinued because of unexpected risk to the volunteers in the study. In light of this experience, it is unlikely that events that would require stopping the study would occur.

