11.3.2 Power Calculation Details

The “TWO SAMPLE FREQ” statement of the SAS version 9.4 (SAS Institute Inc., Cary, NC) “POWER Procedure” was used to conduct the first portion of the power analysis. As user input, the infection rates for the primary and secondary RV challenges were specified as 0.90 and 0.65, respectively. A zero difference in the infection rates of the primary and secondary RV challenges was specified as the null difference and the alternative difference was specified as a 0.25 unit reduction (i.e., $0.90 - 0.65$) in the secondary RV challenge infection rate compared to the primary challenge infection rate. In accordance with the alternative hypothesis “less than” direction, an $\alpha=0.025$ one-sided type I error rate was specified, and the group sample sizes were specified as $n=80$ for the primary RV challenge and $n=35$ for the secondary RV challenge. Based on this set of input parameters, a sample size of 35 volunteers per re-challenge should provide a statistical test with at least 85% power (with a one-sided $\alpha=0.025$ type I error rate) to detect a reduction of as small as 28% (i.e., $[(0.90-0.65)/0.90 \times 100\%]$) between the infection rate following primary challenge and the infection rate following secondary challenge.

The “ONE CORR” statement of the SAS version 9.4 “POWER PROCEDURE” was used to conduct the second portion of the power analysis. As user input, the null correlation was specified to be zero and the alternative correlation was specified to be 0.46. The test statistic was specified as the “Fishers z statistic”, and the two-sided type I error rate (α) was specified as $\alpha=0.05$. Based on this set of input variables, the power to detect a correlation of 0.46 in absolute magnitude is 0.81.

The rationale for the number of subjects screened is as follows:

- 750 volunteers will be screened for antibody to provide approximately 120 volunteers who are seronegative to both RV-16 and RV-39.
- Of the 120 resulting seronegative volunteers, approximately 96 will have a matched RV tetramer available for the T-cell studies.
- 80 eligible subjects (after review of other inclusion/exclusion criteria) will be challenged with RV-16, approximately 72 (90%) will be infected.
- 70 subjects (35 per virus) will be rechallenged with either RV-16 or RV-39.

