11.5 Analysis Plan

11.5.1 General Statistical Plan

General statistical support related to the primary outcome measure, and many of the parameters assessed under exploratory objectives will be provided by [name], MS (Pstat® Accredited Senior Biostatistician, Department of Public Health Sciences). Analyses performed by [name] will include, but are not limited to: (a) comparing infection rates resulting from primary challenge with RV-16 and re-challenge with RV-16 or RV-39, (b)

comparing RV-specific T-cell numbers before and after primary RV-16 challenge, (c) examining correlations between specific T-cell numbers and quantitative shedding as assessed by culture and qPCR as well as the time to virus shedding, (d) comparing clinical outcomes (e.g., cytokine response, and symptom scores) between primary RV challenge and RV re-challenge, and (e) examining correlations between RV specific T-cell numbers and clinical outcomes.

11.5.2 Primary Outcome Analyses (Correlation between the number of pre-existing RV-16 specific T-cells (15 wks.) and infection following re-challenge with RV-39 as assessed by virus shedding in nasal lavage)

Infection rates at primary challenge and the infection rates at secondary challenge will be analyzed by way of a binomial generalized estimating equation (GEE) model [37]. The GEE model response variable will be a binary indicator variable that will be assigned the value 1 if the volunteer is deemed infected on RV challenge and the value 0 will be assigned otherwise. The GEE model predictor variable will be 3 level classification variable. One level will differentiate the primary RV-16 challenge outcome data from the secondary RV challenge outcome data, a second level will identify the secondary RV-16 challenge outcome data, and the third level will identify the secondary RV-39 challenge outcome data. Since we expect that approximately 90% of the volunteers who undergo the primary RV-16 challenge will be eligible to undergo either RV-16 or RV-39 re-challenge, we cannot legitimately assume that the primary challenge infection status and re-challenge infection status of the volunteers who undergo re-challenge are statistically independent. To account for possible *intra-subject* measurement correlation, the components of the GEE model variance and covariance matrix will be estimated by the Huber and White sandwich estimator [38, 39].

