With regard to hypothesis testing, the GEE version of the Wald test will be used to test whether the log-odds for infection is the same for the primary RV-16 challenge and the RV-16/RV-39 re-challenge. The Wald test will also be utilized to test whether the log-odds of infection is the same for the RV-16 and RV-39 re-challenges. For the primary challenge versus re-challenge comparisons, a 0.025 one-side decision rule will be utilized as the null hypothesis rejection criterion, while for the RV-39 re-challenge versus RV-16 re-challenge comparison, a two-sided 0.05 decision rule will be utilized as the null hypothesis rejection criterion. With regard to odds ratio confidence interval construction, the GEE version of Wald confidence interval will be utilized to estimate the lower and upper limits of the 95% confidence interval. The relationship between the number of pre-existing RV-16 specific T-cells (15 wks.) and infection following re-challenge with RV-39, as assessed by virus shedding in nasal lavage, will be quantitatively expressed in terms of the Pearson Product-Moment correlation coefficient if the bivariate normal assumption is deemed creditable based on the observed data, or quantitatively expressed in terms of the Spearman Rank correlation coefficient if the bivariate normal assumption is not supported by the observed data. In either case, the pivotal quantity for the null hypothesis test that the true correlation coefficient is equal to zero will be the Fishers z-statistic, and a two-side $p \leq 0.05$ decision rule will be utilized as the null hypothesis rejection criterion. Confidence interval construction for estimating the underlying correlation coefficient will be based on the Fishers z-transformation method [40].

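### The GEE comparison of primary and re-challenge infection rates does not say which of three infection definitions it uses, and the one in 8.3.1 names the wrong virus for every RV-16 challenge.

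*Combined protocol and SAP*

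**What the plan says.** Three sections of the combined protocol and SAP say who counts as infected.

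- **3.2.1, primary outcome measure:** "Infection will be defined as one positive RV culture obtained in the 5-day time interval after virus re-challenge at Week 15". This is culture only, and the first challenge is not mentioned.
- **8.2.3, assessment of infection and illness:** volunteers with challenge virus found by culture or PCR on Days 1-5, and/or who "have a four-fold rise in neutralizing antibody titer to the study virus are considered infected". The same section defines virus shedders by culture of the challenge virus alone.
- **8.3.1, virology:** subjects with a positive culture for the challenge virus, or with "at least a four-fold rise in antibody titer to RV type 39 are considered infected". PCR is not part of this rule.

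The GEE model in 11.5.2, repeated in 11.5.3, compares infection rates at primary challenge and at each re-challenge. Its response is "assigned the value 1 if the volunteer is deemed infected on RV challenge", with no reference to any of the three definitions. For primary versus re-challenge, "a 0.025 one-side decision rule will be utilized as the null hypothesis rejection criterion".

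Section 11.3.2 powers this comparison: "the infection rates for the primary and secondary RV challenges were specified as 0.90 and 0.65, respectively", and "the group sample sizes were specified as $n=80$ for the primary RV challenge and $n=35$ for the secondary RV challenge". No definition is attached to the 0.90. Section 2.2 gives infection rates of 80-90% for the model, and 9.2.1 states that "the expected infection rate for volunteers in the study is 85-90" per cent. Neither says how infection was ascertained.

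**The concern.** Section 11.3.1 treats a lower infection rate at re-challenge as something to establish before the T-cell relationship is examined, and sizes the study partly on it. That comparison needs one definition, applied alike at both challenges. Here the analyst can choose among three, and 5.4.2 says the study involves no masking procedures (only the volunteers are not told which virus they receive).

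The choice affects how individuals are classified. Section 5.4.1 gives RV-16 to everyone at first challenge, and one re-challenge arm receives it again. A four-fold rise to RV-39 is not a marker of RV-16 infection. The background section also shows that culture and serology can disagree: two culture-positive pilot subjects had not seroconverted by day 21.

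**Working it through.** **1. Which limbs of each definition can detect infection, by challenge**

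| Definition | First challenge, RV-16 (80) | Re-challenge, RV-16 (35) | Re-challenge, RV-39 (35) |
|---|---|---|---|
| 3.2.1 | not covered | culture | culture |
| 8.2.3 | culture, PCR, RV-16 rise | culture, PCR, RV-16 rise | culture, PCR, RV-39 rise |
| 8.3.1 as written | culture only in effect | culture only in effect | culture, RV-39 rise |

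The last row assumes that an RV-16 infection does not ordinarily produce a four-fold rise to RV-39. The RV-39 wording fits 35 of the 150 planned challenges and does not fit the other 80 + 35 = 115.

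**2. Direction of bias under 8.3.1.** The first challenge and the RV-16 re-challenge are in effect scored by culture, so that contrast is even-handed. The RV-39 arm has an extra route to being scored infected. Its rate can only go up relative to culture alone, so the fall from primary challenge to RV-39 re-challenge is understated. The RV-16 versus RV-39 re-challenge test is tilted the same way, with RV-39 looking more infectious.

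**3. Direction of bias under 8.2.3.** Subjects enter with titres of 1:2 or below (5.2). If the first challenge raises RV-16 titres and they are still raised at Week 15, a further four-fold rise is harder to achieve in the RV-16 arm. Infections could then be under-detected there, but only among subjects negative by both culture and PCR. The documents give no count of such subjects, so no size can be attached.

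**4. The T-cell correlation.** Section 3.2.1 specifies culture, 11.5.2 analyses infection through virus shedding in nasal lavage, and 8.2.3 defines shedders by culture. These agree. The correlation power in 11.3.2 (0.81 at r = 0.46) does not use the 0.90 rate.

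**5. Reproducing the stated power.** Inputs from 11.3.2: p1 = 0.90, p2 = 0.65, n1 = 80, n2 = 35, one-sided 0.025. Pearson two-proportion test with pooled null variance, groups treated as independent:

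power = Φ{[(p1 − p2) − 1.96·s0] / s1}, with s0 = √[p̄(1 − p̄)(1/n1 + 1/n2)] and s1 = √[p1(1 − p1)/n1 + p2(1 − p2)/n2].

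- p̄ = (80 × 0.90 + 35 × 0.65)/115 = 0.824
- s0 = 0.0772; s1 = 0.0873
- z = (0.25 − 1.96 × 0.0772)/0.0873 = 1.13
- power = 0.871, consistent with the stated figure of at least 85%

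**6. Sensitivity over the plan's own 80-90% range.** The relative reduction is 0.25/0.90 = 27.8%.

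| Primary rate | Re-challenge rate, same relative reduction | Power | Re-challenge rate, same 0.25 drop | Power |
|---|---|---|---|---|
| 0.90 | 0.650 | 0.87 | 0.65 | 0.87 |
| 0.85 | 0.614 | 0.78 | 0.60 | 0.82 |
| 0.80 | 0.578 | 0.69 | 0.55 | 0.78 |

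**The case against.** The strongest reply is that the primary outcome measure is the T-cell correlation, which is consistently culture-based, and that the GEE contrast is a preliminary step. That stands. A reader might infer that every primary analysis lacks a defined endpoint; the documents do not support this. Nor is it a gap for the correlation that 3.2.1 covers re-challenge only, since that outcome arises only there.

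A reader might also infer that 8.3.1 lowers the re-challenge rate and so manufactures protection. Read literally it does the opposite, because it adds detection only in the RV-39 arm.

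The 115 of 150 count should not be read as misclassified outcomes. The culture limb covers every challenge, 8.3.2 tests sera against both viruses, and 8.2.3 names the study virus. The RV-39 wording resembles the rule of the RV-39 pilot described in the background and may have been carried over from it.

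The reference in 3.2.1 to any RV culture is not a live problem either: 11.3.2 excludes from analysis volunteers who shed an RV other than the challenge virus.

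Finally, the power statement is not an error. It reproduces, and 0.90 lies within both ranges that the plan quotes. The pilot's 12 of 16 (75%) infected is not evidence of a low culture-only rate: it was scored by culture or seroconversion, after RV-39, in 16 subjects, three of whom had evidence of recent RV exposure.

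What survives is that the GEE response cites no definition and that the 8.3.1 rule is wrong for RV-16. A reasonable inference about what was meant does not replace a stated rule.

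**Conclusion.** The point holds for the GEE contrast of primary versus re-challenge infection rates. Three definitions conflict and the model selects none. Section 8.3.1, applied as written, scores a culture-negative RV-16 seroconverter as uninfected while counting RV-39 seroconverters in the heterologous arm, which biases the contrast against showing cross-protection. The size of that bias cannot be computed, because the documents give no infection rates by definition. The opposite effect possible under 8.2.3 is an inference about baseline titres and is likewise unquantified.

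On power, the conclusion is one of sensitivity. The stated figure is right for its inputs. Over primary rates of 0.90 to 0.80 it runs from 0.87 to 0.69 at a constant relative reduction, or from 0.87 to 0.78 at a constant absolute drop. These figures assume independent groups of 80 and 35 and the same definition at both challenges.

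**What to change.** - **11.5.2 and 11.5.3:** define the GEE response, for both challenges, as at least one positive culture for the challenge virus on Days 1-5. This matches the primary outcome in 3.2.1.
- **8.3.1:** replace the reference to RV type 39 with the challenge virus, and align the rule with 8.2.3.
- **8.2.3:** keep the composite of culture, PCR and seroconversion for defining symptomatic infection, and use it as a labelled sensitivity analysis of the GEE.
- **11.3.2:** state which definition the 0.90 refers to, and show power for primary rates across 80-90%, as in the table above.

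The cost is wording and a somewhat less favourable power range. No new specimens are needed, since cultures, PCR and sera are already scheduled at both challenges.
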